- 3) The COPE Inventory (COPE; Carver et al., 1989) assesses 14 conceptually distinct coping strategies. It includes 13 scales with four items each and one single item question to assess different strategies for coping with stress. All items are reported on a 4-point scale (1 = I usually don't do this at all; 2 = I usually do this a little bit; 3 = I usually do this a medium amount; 4 = I usually do this a lot). The COPE inventory has been tested previously and found to have good psychometric properties (Carver et al., 1989; Stone, Greenberg, Kennedy-Moore & Newman, 1991). We will also incorporate 4 exploratory, yoga-related items to the COPE Inventory: (1) I take several deep, calming breaths, (2) I breathe deeper and calmer, (3), I focus on my breathing, (4) I concentrate on my breath.
- 4) The Insomnia Severity Index (ISI; Morin, 1993) is designed to be both a brief screening measure of insomnia and an outcome measure for use in intervention research. The index contains seven items including the severity of sleep onset and maintenance (e.g., middle and early morning awakening) difficulties, satisfaction with current sleep pattern, interference with daily functioning, appearance of impairment attributed to the sleep problem, and the degree of concern caused by insomnia. The items are rated on a five-point Likert scale from 0 (not at all) to 4 (extremely). It has shown good internal consistency (Cronbach's alpha of .76; Bastien, Vallières, & Morin, 2000). We will also include one exploratory question: With focus on the past week, how many hours did you sleep at night: a) During a typical weekday (Monday to Friday)? b) During Saturday or Sunday?
- 5) Diet is a 2-item measure that is used as an exploratory questionnaire. The questions are as follows: Have you changed your eating habits since you started your participation in the study? Categorical answer choices include 1) No, not at all, 2) Yes, to some extent, 3) Yes, to a great extent. A second question is open-ended: If you have changed your eating habits, please describe how. This very brief questionnaire will be given only once at the end of the study to explore whether dietary changes have occurred following the 5-week study period.
- 6) General Health Questionnaire (GHQ; Goldberg & Williams, 1988) consists of 12 items, each one assessing the severity of a mental problem over the past few weeks using a 4-point Likert-type scale (from 0 to 3). These scores generate a total score ranging from 0 to 36. The positive items are corrected from 0 (always) to 3 (never) and the negative ones from 3 (always) to 0 (never). Higher scores indicate worse health. The instrument is considered as reliable and has been translated into 38 different languages. The reported Cronbach alpha coefficient for the GHQ is a range of 0.82 to 0.86 (Goldberg, & Williams, 1988).
- 7) The Harmony in Life Scale (HILS; Kjell et al., in press) assesses a global sense of harmony in one's life and consists of 5 statements (e.g., "Most aspects of my life are

in balance”) for which participants are asked to indicate degree of agreement on a 7-point Likert scale (1 = strongly disagree, 7 = strongly agree). The harmony score is established by summarizing the 5 statements for each participant. It has shown high internal consistency (Cronbach’s alpha of .91; Garcia et al., 2013).

- 8) The Life Satisfaction Scale (LSS) consists of three items rated on a 7-point scale. The scale has previously been reported to have good internal consistency ($\alpha = .90$; Ahlerup, 2015).
- 9) The Kentucky Inventory of Mindfulness Skills -Short Version (KIMS; Baer, Smith, & Allen, 2004; Höfling, Ströhle, Michalak, & Heidenreich, 2011) is a 20-item multi-dimensional scale of interrelated skills related to what one does while practicing mindfulness, and how one does it. The “what” skills include observing (noticing or attending to) current experience, describing (noting or labeling observed experiences) with words, and participating (focusing full attention on current activity); the “how” skills include being nonjudgmental (accepting, refraining from evaluation), being one-mindful (using undivided attention), and being effective (using skillful means; Baer et al., 2008). The subscales show good internal consistency with alpha coefficients ranging from .80 to .85.
- 10) The Brief Experiential Avoidance Questionnaire (BEAQ; Gámez et al., 2014) consists of 15 items used to assess behavioral avoidance (situational avoidance of physical discomfort and distress), distress aversion (non-acceptance of or negative attitudes toward distress), procrastination (delaying activities that may cause distress), distraction/suppression (attempts to ignore or suppress distress), repression/denial (distancing and dissociating from distress), and distress endurance (willingness to engage in behavior that is consistent with one’s values even when in distress). Items are rated on a 6-point scale ranging from 1 (*strongly disagree*) to 6 (*strongly agree*). The scale shows evidence of good internal consistency with alpha coefficients ranging from .80 to .89 (Gámez et al., 2014).
- 11) The Yogic Breathing as Stress Coping Scale. We constructed a 4-item measure, the Yogic Breathing as Stress Coping Scale (YBSC), to evaluate how often individuals use breathing as a coping strategy when they experience a stressful event. The instruction, *What do you generally do when you experience stressful events?* was adapted from the COPE scale (Carver et al., 1989). The four items are as follows: *I take several deep, calming breaths; I breathe deeper and calmer; I focus on my breathing; I concentrate on my breath.* The four items are rated on a five-point Likert scale from 1 (I usually don’t do this at all) to 5 (I usually do this a lot).

Participants will be asked to wait (if needed) until a total of 2 hours have passed since their fasting glucose tolerance test, so that a 120-minute measurement of plasma glucose concentration can be acquired. Following this, participants will be invited to a quiet area/room where breakfast will be provided free of charge. After breakfast, participants will complete the psychological measures and be instructed by a Clinical Research Unit staff member on how to use the sphygmomanometer described above (the portable, digital blood pressure machine). Participants will also be given a container with lid to collect a fecal sample at home. Prior to leaving their appointment, participants will be given an information letter about their yoga practice (Please see Appendix 4:3-4:5), and they will be given a free yoga mat to bring to class (exception: Control group participants will receive their yoga mat

during the workshop, please see below). Participants are asked to return the sphygmomanometer and fecal sample to the Clinical Research Unit the following day.

3. Yoga Interventions – 5 weeks

Group 1: Stress education + Yoga (SED_YOGA)

Stress education + Yoga brings together education about stress, mindfulness and yoga practice. It will involve weekly group meetings, homework (please see Appendix 4:6), and yoga postures. Stress education and mindfulness will make up one portion of the intervention. This will take place in a group lecture format and shall be conducted by a mental health professional(s). Yoga practice in a group format will make up the second portion of the intervention. The word yoga means ‘to yoke’ or ‘unite’ in the sense that it is a practice of connecting the mind with the body. Yoga thus focuses on mental and physical strength building exercises and postures, and in this study, will be lead by a trained yoga instructor(s). More specifically, yoga practice will involve controlled breathing, prescribed body positions, and meditation, with the goal of attaining a state of relaxation. Instructors will lead yoga practitioners in and out of yoga postures (poses) verbally throughout the sessions. Stress education + Yoga will be held 2x/week in the evenings for 5 weeks.

Group 2: Yoga only (YOGA)

The Yoga only group will include the same yoga practice as described above for Group 1, but it will not include the stress education component.

Group 3: Control (CONTROL)

The control group will not participate in any yoga practice for the duration of the research study. However, because these participants had indicated moderate to high levels of stress during study recruitment, we want to provide them with an introduction to yoga, after the study is completed. Therefore, each control group participant will be invited to a 3-hour yoga workshop directly following the 5-week study period. This workshop will include education about stress and mindfulness as well as an introduction to yoga practice. Similarly to Groups 1 and 2, participants in the Control group will receive a free yoga mat.

Approximately one week before the yoga intervention is due to end, participants will receive a letter by mail indicating their second appointment time at the Clinical Research Unit (please see Appendix 4:7-4:8).

4. Second Appointment at Clinical Research Unit (post-testing)

At the follow up measurements, after the 5-week yoga practice, the participants will again be invited to the Clinical Research Unit at Skånes University Hospital in Malmö and have the same physiological measures taken as in the the first appointment. They will also fill out the same survey with psychological measures as they did at the first appointment. Breakfast will again be offered following completion of the measures. Finally, participants will be thanked for their participation in the research study.

Required sample size and a priori power analyses

The main statistical analyses will be regression analyses by estimating the models with full-information maximum likelihood (FIML) in AMOS software allowing to perform Intent-To-Treat analyses. The outcome variables will be all study variables calculated as the difference between pre-test and post-test scores.

Mediation models will be tested with the macro PROCESS by Preacher and Hayes (2008) which implements a bootstrapping procedure to create confidence intervals for indirect effects in the mediation model.

G*Power, 3. 1. 7 (Faul, Erdfelder, Lang, & Buchner, 2007) was used to calculate a priori power for analyzing main effects. Assuming that the effect is medium size ($f = 0.25$; see Cohen, 1988), a significance level is of $\alpha = .05$, and the power values of the F tests are .95, a total of $N = 105$ must be recruited.

Ethical Considerations

This research will follow the ethical guidelines regarding informed consent and confidentiality as specified by etikprövningslagen (2003:460). All participants will be informed of the study's aim and method, both orally and in writing, as well as sign an informed consent document prior to participation (see Appendix 4:1-4:2). They will be informed that their participation is completely voluntary and that they can discontinue participation at any time, without giving a reason. Contact information for the project leader will be provided to answer any questions.

The name of each participant will be registered on a single master list in combination with a numerical code. The list will be kept in a locked closet at the Clinical Research Unit at Skånes University hospital in Malmö, stored apart from other study documents. Numeric codes will be used throughout the research on all study documents to identify participants, in order to preserve confidentiality. Once data have been collected, the list with participants' names will be destroyed, ensuring that the identity of the participants will remain undisclosed. No individual names will ever be included in the data file. All study documents will be kept in locked closets, and contain no person names. The data used to assess the inclusion / exclusion criteria in the study (see above), will not be saved for participants excluded from the study. Any data collected from participants choosing to discontinue the study will be destroyed.

Bio-banking and laboratory analysis: Region Skåne biobank BD53 ([contact]) will be the biobank used in this study to store biological samples (i.e., blood serum and plasma, fecal samples). The biobank utilizes a freezer (-80 degrees) where biological samples are kept frozen until the time of analysis. Samples are not marked with a person's name or social security number, but with a numerical code that can only be connected to the participant (described above). Biological samples will be subsequently analyzed at the Department of Clinical Sciences, Faculty of Medicine, Lund University. The person responsible for bio-banking and laboratory analysis of biological samples is [name], Clinical Research Unit, Department of Clinical Sciences, Skåne University Hospital, Malmö, T: [name].

One possible risk of participating in this research is that individuals may experience some distress in participating in the study measurements. Blood sample collection and glucose tolerance testing require participants to come to their appointment in a fasting state. This

may cause some people to experience hunger and/or fatigue. To minimize discomfort, appointments are made in the early morning and blood collection will be among the first procedures performed. Participants will receive breakfast for free after the study measurements are complete.

Another possible risk is that some participants may experience discomfort with the venipuncture procedure. To minimize this risk, blood collection will only be performed by licensed medical staff at the Clinical Research Unit, Skånes University hospital.

Fasting and 120-minute glucose tolerance test requires participants to drink a liquid containing glucose (sugar) between their first (fasting) and second (120-minute) blood samples. This may cause some participants to feel nervous or anxious about ingesting a liquid. However, the drink is merely sweet, and there are no known risks from participating in a glucose tolerance test.

An electrocardiogram will be performed by a member of the Clinical Research Unit, which may cause some people to feel nervous or embarrassed about having electrodes attached to their upper torso and limbs. However, the electrical signals that are recorded by the machine in reading the activity of the heart are painless. It only requires the participant to lie down and remain still for a few minutes.

Participants may also experience some anxiety or embarrassment about having to produce a fecal sample. However, this is a normal bodily function that causes no harm. Participants will be given the option of giving the sample while at the hospital or, alternatively, in the privacy of their home (and returning the sample the following day). Staff at the Clinical Research Unit are routinely handling biological samples, so it will not appear as an abnormal process.

Participants will be informed about all abovementioned physiological study procedures during the recruitment and informed consent process. They are free to decline participation in this study for any reason. Participation is completely voluntary.

Participants will receive feedback on their results for all physiological measurements that have clinically accepted parameters. This includes information on blood pressure, plasma glucose & lipids and electrocardiogram results. Participants will not receive feedback on exploratory measures since there are no established clinical parameters. This includes all blood sampling procedures, pulse-wave velocity, heart-rate variability and gut microbiota fecal sampling. This information will be made known in the recruitment and informed consent process.

Filling out psychological measures may cause distress for some participants. If this occurs, participants have contact information to the project leader who can answer questions about the study. Further, they will be filling out the questionnaires at the Clinical Research Unit at Skånes University hospital. Should any mental distress occur to the point of requiring emergency assistance, the Unit staff (which includes licensed nurses and physicians) can refer the person to the Emergency Department at the hospital. The risk for severe distress while filling out questionnaires however is probably low. The measures selected for the study are well-validated and have been used in many previous studies.

Computer Security: Participants will be asked to use a University secured computer to complete psychological measures. Computers are property of the research team. Psychological measures on the computers are configured to a private web-survey that is password protected and only the research team can access. Participants will log-in with their study numeric code and not any other identifying information. When data are transmitted through the web-survey from the participant to the research team, they will be stored on a computer that is not connected to the internet.

Another possible risk in the study is that participants may physically hurt themselves during yoga practice. To limit this risk, participants with any known physical limitations that may prevent light physical activity (yoga postures) will be excluded from participation (please see Exclusion criteria). Also, as the yoga sessions in this study are at the beginners level, led by a trained yoga teacher(s) and suitable for novice practitioners, we perceive the risk for physical injury to be small.

Last, it is possible that the participants assigned to the Control group (i.e. those who will not receive stress education and/or yoga during the 5-week study period) will be dissatisfied. We will explain to the participants the methodological necessity of having a Control group, to be able to assess the health benefits of yoga methodologically. We will also arrange for a 3-hour workshop for Control group participants, directly after the study period, which will provide them with stress education, mindfulness and yoga practice, as well as a free yoga mat.

References

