Recruitment will be accomplished in two ways, 1) via telephone, and/or 2) in person. Telephone recruitment will be directed to participants in the Malmö Offspring Study (MOS) as described above. For individuals in MOS indicating a chronic experience of stress within the past year, information letters will be sent (see Appendix 3). Then they will be contacted by a person employed by the research project. During the telephone call, information about

the current yoga study, as described in the information letter in the Appendix 3 and Appendix 4:1 will be given, and the person will be asked if he/she is interested in participating. The telephone interviewer will also ask questions related to the inclusion/exclusion criteria described below. In-person recruitment will be directed to individuals visiting the Clinical Research Unit at Skånes University Hospital in Malmö who indicate high stress to the personnel. They will be orally given the same information as during the telephone interview previously described. Recruitment will take place over an approximate 2-month period.

Inclusion criteria:

1. A score on four items of the Perceived Stress Scale (PSS; Cohen et al., 1983) between 8-16, thereby indicating a current stress experience of at least moderate level (please see Appendix 5:12).
2. Ability to participate in the intervention during the time-period.
3. Comprehensive in Swedish (the intervention will be in Swedish).

Exclusion criteria

1. Ongoing yoga practice or any regular practice of yoga or meditation within the last 6 months.
2. Any known physical limitations that may prevent light physical activity (yoga postures).

When a person qualifies for the study, an appointment will be scheduled for him/her to come to the Clinical Research Unit at Skånes University Hospital in Malmö for the initial tests to be taken (see Measures below). The name of each participant will only be registered on a single master list in combination with a numeric code to ensure participant anonymity (please see Ethical Considerations below for further detail). Numeric codes will be used throughout the remainder of the study to identify participants. Additionally, the master list will provide the randomly generated number indicating which study group he/she is assigned to. Each person will be randomized at the individual level to one of the following conditions:

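### Both yoga arms are taught in groups, but the regression, the mediation bootstrap and the sample size make no allowance for correlation within class

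*Combined protocol and SAP*

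**What the plan says.** The recruitment and screening part of the Procedure sets the unit of allocation: "Each person will be randomized at the individual level to one of the following conditions".

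The section on the yoga interventions then describes delivery. For SED_YOGA, stress education is one portion: "This will take place in a group lecture format and shall be conducted by a mental health professional(s". The other portion is yoga: "Yoga practice in a group format will make up the second portion of the intervention". The yoga "will be lead by a trained yoga instructor(s", an optional plural that leaves the number of instructors open. For the second arm, "The Yoga only group will include the same yoga practice as described above for Group 1", without the stress education. Both arms meet twice a week over five weeks, so ten sessions. For the third arm, "The control group will not participate in any yoga practice for the duration of the research study"; its workshop comes afterwards.

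The section on sample size and power holds the whole analysis plan: "The main statistical analyses will be regression analyses by estimating the models with full-information maximum likelihood (FIML) in AMOS software", with pre-to-post change in every study variable as the outcomes. Mediation is tested with PROCESS bootstrap intervals. The sample size is a G*Power F test at f = 0.25, alpha .05 and power .95, giving N = 105. The Participants section plans about 120.

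No section mentions class, instructor effects, ICC, design effect, a multilevel model or robust standard errors. The number of classes, their size and the number of instructors are not given.

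**The concern.** Randomising individuals makes the arms comparable at baseline, but it does not keep outcomes independent afterwards. People who share a teacher, a room and a group for ten sessions may come to resemble one another in their change scores. Here that can happen in two arms and not in the third.

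FIML deals with missing outcomes, not with clustering. A regression with no class term counts each class member as a full independent observation. A bootstrap that resamples individuals does the same for the indirect effects. If the within-class correlation is positive, confidence intervals are too narrow and false-positive findings more frequent than .05. The exposure is greatest where both sides of a contrast are clustered.

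**Working it through.** **The plan's own figure.** For a one-way F test on the change score with three arms, f = 0.25 and alpha .05 (noncentrality f² × N = 0.0625 × N), 95% power needs N = 252; N = 105 gives 61% and N = 120 gives 68%. The stated 105 appears only under settings the text does not give, for example a group-by-time interaction with a pre-post correlation of about .18. That is a separate matter. What counts here is that none of these routes includes a design effect.

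**Inputs.** From the documents: individual randomisation, three arms, about 120 people, two group-taught arms and one without sessions. Assumed: 1:1:1 allocation (40 per arm), equal fixed classes that do not mix arms, ICC 0 to .10, equal total variance across arms, no dropout. Classes of 10 to 20 mean 40/20 = 2 to 40/10 = 4 classes per yoga arm.

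**Formulas**, with m people per class:
- design effect in a yoga arm: DE = 1 + (m − 1) × ICC
- variance inflation, yoga arm versus control: (DE + 1)/2
- variance inflation, SED_YOGA versus YOGA: DE
- ratio of true to naive standard error: square root of the inflation
- true type I error: 2 × [1 − Φ(1.96 / ratio)]

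Worked case, m = 15 and ICC .05: DE = 1 + 14 × .05 = 1.70. Versus control: (1.70 + 1)/2 = 1.35, ratio 1.16, error .092. Between yoga arms: 1.70, ratio 1.30, error .133.

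| Class size | ICC | DE | SE ratio, yoga vs control | SE ratio, yoga vs yoga | Error, yoga vs control | Error, yoga vs yoga | Error, 3-arm F test (simulated) |
|---|---|---|---|---|---|---|---|
| any | 0 | 1.00 | 1.00 | 1.00 | .050 | .050 | .05 |
| 10 | .01 | 1.09 | 1.02 | 1.04 | .055 | .060 | .06 |
| 10 | .05 | 1.45 | 1.11 | 1.20 | .077 | .104 | .10 |
| 15 | .05 | 1.70 | 1.16 | 1.30 | .092 | .133 | not run |
| 20 | .05 | 1.95 | 1.21 | 1.40 | .107 | .160 | .16 |
| 20 | .10 | 2.90 | 1.40 | 1.70 | .160 | .250 | .27 |
| 40 (one class) | .05 | 2.95 | 1.41 | 1.72 | .163 | .254 | .27 |
| 40 (one class) | .10 | 4.90 | 1.72 | 2.21 | .254 | .376 | .44 |

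The last column comes from 20,000 simulated trials per row with 40 per arm and does not rely on the normal approximation.

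**Sample size.** Taking 105 at face value (35 per arm) and inflating only the yoga arms: with m = 10 and ICC .01, 35 × 1.09 rounds up to 39, so 35 + 2 × 39 = 113. With m = 10 and ICC .05, 35 × 1.45 rounds up to 51, so 137. With m = 20 and ICC .05, 35 × 1.95 rounds up to 69, so 173. If each arm is one class, adding people to it does not help, because class and arm coincide.

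**The case against.** The strongest reply is that the harm is conditional. No document gives an ICC, and at the low end (classes of 10, ICC .01) the error versus control is .055, practically nominal. This stands: a reader might infer that the standard errors are too small as a matter of fact, and the documents do not show that.

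Second, the plan never calls its regression single-level and lists no predictors; it is silent on class. That is also right, but a plan that names no class term, followed as written, treats class members as independent.

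Third, the class structure is partly inferred. The text does not say that people stay in one class or that the arms never share one, and the participant letters in Appendix 4 that may describe scheduling are not in the text available. If the arms shared yoga classes evenly, yoga-class effects would largely cancel in SED_YOGA versus YOGA. The figures for that contrast therefore rest on separate classes. The plan also does not name that contrast; its power statement is for an F test, which is why the simulated F-test column is shown.

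Fourth, a reader might infer that instructor is confounded with arm, or that both yoga arms share a lecturer. Neither is supported: the number and assignment of instructors are left open, and only SED_YOGA has lectures.

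Finally, a single ICC range is applied to outcomes as different as questionnaires and blood markers. It is a range for illustration, not an estimate.

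**Conclusion.** The point holds in conditional form. Group delivery in two of three arms is stated, and no part of the analysis or the sample size allows for it. If outcomes correlate positively within class, standard errors for contrasts involving a yoga arm are understated.

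Under the assumptions listed, the understatement for a yoga arm versus control runs from 2% (ratio 1.02) to 40% (ratio 1.40), and for SED_YOGA versus YOGA from 4% to 70%. One class of about 40 per arm would be worse still and would also leave class inseparable from arm. The omission is certain; its size is not. It should be corrected, but it does not by itself show that any result would be wrong.

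**What to change.** 1. State the number and size of classes and the number of instructors per arm. Record class and instructor for each yoga participant under the numeric code, using the same label if the arms share a class. Do this before the name list is destroyed at the end of data collection, as Ethical Considerations provides.
2. Prespecify a likelihood-based, partially nested mixed model: random class effect in the yoga arms only, arm-specific residual variance, and Kenward-Roger or Satterthwaite degrees of freedom. Model pre-test and post-test jointly, so that randomised participants with a missing post-test stay in, as FIML intended. Ethical Considerations also says that data from people who discontinue are destroyed, which limits any intent-to-treat analysis and needs separate attention.
3. If an arm has only one or two classes, report the planned regression with its standard errors multiplied by the ratios above over a stated ICC range, such as 0 to .10, and say that class and instructor effects cannot be separated from arm.
4. State that the PROCESS intervals are subject to the same issue and that N = 105 makes no allowance for clustering.

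The cost in data is small: class and instructor codes. The cost in precision is not always small. With two classes per yoga arm, SED_YOGA versus YOGA has about 4 − 2 = 2 class-level degrees of freedom, and the critical t is about 4.3 instead of 1.96, which is why step 3 is needed.

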The primary purpose of this study is to evaluate the effects of yoga on: 1) psychological health, specifically measured as stress level, stress coping strategies, depression, anxiety, well-being, life harmony, diet, and sleep quality; and 2) physiological health, specifically measured as blood plasma and serum stress markers (e.g., hormones, inflammation), blood plasma stress-related indicators (i.e., metabolic and cardiovascular function), and non-invasive clinical measures of stress-related indicators (i.e, cardiovascular and autonomic nervous system function) including blood pressure, arterial stiffness (via pulse wave velocity), and heart rate variability (via electrocardiogram), as well as digestive health via gut microbiota fecal sampling. Further, we intend to explore whether any changes in coping strategies (breathing, mindfulness) as a result of yoga practice may correspond to predictable changes in well-being.

Method

Participants

We plan to conduct a randomized controlled field experiment. In order to properly evaluate the effects of the intervention statistically, we will recruit approximately 120 individuals (please see power analysis below). Study participants will be recruited primarily from the ongoing Malmö Offspring Study (MOS; Dnr 2012/594) which takes place at the Clinical Research Unit at Skånes University Hospital in Malmö (Klinisk Forskningsavdelning på Skånes universitetssjukhus i Malmö). MOS is an inter-generational study where all children and grandchildren of individuals in the Malmö Diet and Cancer Cardiovascular Cohort (MDC-CC; n=6103) are invited to participate. The MDC-CC is a population-based study that investigates the epidemiology of carotid artery disease (LU 51-90 and Dnr 2009/633; Melander, et al., 2009, 2012). Individuals participating in MOS who have indicated an experience of chronic stress during the past year will be contacted by the research team. Other individuals visiting the Clinical Research Unit and/or members of the community are also eligible to participate in the study according to the inclusion/exclusion criteria (please see below).

Procedure

1. Telephone and In-Person Recruitment and Screening

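### Outcomes are raw pre/post differences and no baseline covariate is specified; adjusting each outcome for its baseline would be at least as precise, at almost no cost

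*Combined protocol and SAP*

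**What the plan says.** The combined protocol and SAP, section *Required sample size and a priori power analyses*, names the estimator: "The main statistical analyses will be regression analyses by estimating the models with full-information maximum likelihood (FIML) in AMOS software", which is meant to allow an intention-to-treat analysis. It then defines the outcomes: "The outcome variables will be all study variables calculated as the difference between pre-test and post-test scores". No list of predictors follows. Baseline is neither named as a covariate nor ruled out.

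The same section sizes the trial for F tests with f = 0.25 and α = .05. It adds that "the power values of the F tests are .95" and concludes that "a total of $N = 105$ must be recruited". Under *Participants* the target is higher: "we will recruit approximately 120 individuals (please see power analysis below". The *Procedure* section randomises individuals to three groups. The second appointment repeats the physiological measures and questionnaires of the first, so a baseline value exists for nearly every outcome. The Diet items are the exception: they are asked once, at the end.

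**The concern.** A regression of the raw difference on group alone assumes that a participant who starts one unit higher is expected to finish one unit higher. Measures that fluctuate usually have a slope below 1, because extreme starting values regress towards the mean. Fixing the slope at 1 then leaves avoidable noise in the outcome. It also lets a chance baseline difference between arms leak into the estimated effect.

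With about 40 per arm (120 / 3, equal allocation assumed), such differences are not negligible. Precision also matters, because the stated power cannot be confirmed from the stated inputs (see the check below).

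A lesser point concerns missing data. If the post-test is missing, so is the difference, and a model without baseline gives FIML nothing else to use for that participant. A model with baseline lets FIML condition on it. This helps only where the baseline record is kept, since *Ethical Considerations* has the data of participants who discontinue destroyed.

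**Working it through.** **Inputs from the documents:** f = 0.25, α = .05, power .95, N = 105, recruitment of about 120, three arms, one post-test after 5 weeks. **Assumed, because the documents do not give them:** equal allocation, full retention, pre/post correlation r of .3 to .7 and, at first, equal pre and post SDs (σ).

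**Step 1. The plan's own figure.** For a three-arm F test on one change score, the noncentrality is λ = N f² with 2 and N − 3 degrees of freedom. Power .95 then needs N = 252 with equal arms, not 105. Power is .61 at N = 105 (λ = 105 × 0.0625 = 6.56) and .68 at N = 120 (λ = 7.5). Values near 105 do appear under settings that the text does not state. One is a 3 × 2 group-by-time interaction with r of about .18 to .19. The stated N is therefore not reproduced, but it is not shown to be wrong either.

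**Step 2. Residual variance with equal SDs.**
- Unadjusted change: 2σ²(1 − r)
- Adjusted for baseline: σ²(1 − r²)
- Ratio: (1 + r)/2, a reduction of (1 − r)/2

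**Step 3. Power at N = 120 with f = 0.25 on the change-score scale.** The adjusted test has λ = 7.5 divided by the ratio, with 2 and 116 degrees of freedom.

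| r | Change variance (σ² = 1) | Adjusted variance | Ratio | Reduction | λ adjusted | Power unadjusted | Power adjusted |
|---|---|---|---|---|---|---|---|
| .3 | 1.40 | 0.91 | 0.65 | 35% | 11.54 | .68 | .86 |
| .5 | 1.00 | 0.75 | 0.75 | 25% | 10.00 | .68 | .80 |
| .7 | 0.60 | 0.51 | 0.85 | 15% | 8.82 | .68 | .75 |

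At N = 105 the same formulas give .61 unadjusted and .81, .75 or .69 adjusted. Simulation with 2,000 trials per setting gave .61, .60 and .64 unadjusted and .80, .73 and .69 adjusted.

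**Step 4. Sensitivity to the scale of f.** If f = 0.25 is in post-test SD units, power at N = 120 rises from .52 to .72, .68 to .80 or .89 to .93 at r = .3, .5 or .7. If the change analysis really had power .95 at N = 105, the adjusted analysis would reach it with about 70, 80 or 90 participants.

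**Step 5. Sensitivity to unequal SDs.** In general the reduction is (SD_pre − r·SD_post)² / Var(change). With SD_pre/SD_post = 0.7:
- r = .3: 0.4² / 1.07 = 15%
- r = .5: 0.2² / 0.79 = 5%
- r = .7: 0%

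If selection cuts the baseline variance to 40% and leaves the slope b unchanged, the reduction is 0.4(1 − b)² / [(1 − b²) + 0.4(1 − b)²]. That is 18%, 12% or 7% at b = .3, .5 or .7.

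**Step 6. Chance imbalance.** With 40 per arm, the standard error of a two-arm baseline difference is √(2/40) = 0.22 SD. At a slope of .5, an imbalance of that size shifts the unadjusted change contrast by (1 − .5) × 0.22 = 0.11 SD. Adjustment removes this shift.

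**The case against.** The strongest reply is that the plan names no predictors at all. A reader might infer that group is the only one, but the text does not say so. If baseline were entered in the regression of change, the group effect and its standard error would equal those of the adjusted post-test, and nothing would be lost. This stands as a limit on the claim: the documents show that adjustment is not specified, not that it is refused. It does not remove the point. An unstated covariate set commits the analyst to nothing and leaves the choice open until the data are seen.

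Second, a reader might take 15% to 35% as a measured loss. It is not. It rests on an assumed r and on equal SDs, and one range cannot describe questionnaires, blood markers, heart rate variability and gut microbiota alike.

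Third, it is tempting to argue that entry on a four-item PSS score of 8 to 16 lowers r and so enlarges the gain. The documents do not support this. Narrowing the baseline range need not lower the slope, and with the slope unchanged it shrinks the gain (step 5). In simulated selection above the mean on a separate screening score, with r = .5 beforehand, the 25% reduction became about 30%, 21% or 17%, depending on how the screen correlated with the two visits. Those correlations are not given. The screen also concerns perceived stress only.

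Finally, the unadjusted change is unbiased over randomisation, so the planned analysis is not invalid.

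**Conclusion.** The point holds as an efficiency improvement that the plan leaves unclaimed. As written, every outcome is a raw difference and no baseline adjustment is specified. Apart from one degree of freedom, adjustment in this randomised design gains precision or leaves it about the same, and it protects against chance imbalance.

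The 35% to 15% reduction, and the rise from .68 to .86, .80 or .75 at N = 120, depend on r = .3 to .7, equal SDs, three equal arms, full retention and f on the change-score scale. For the PSS itself the gain may be smaller, possibly near zero, if selection has narrowed the baseline spread.

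A reader might also conclude that true power is well below .95. The documents do not settle that, because neither the scale of f nor the test behind N = 105 is stated. That question is separate and larger, and this point does not depend on it.

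**What to change.** Replace the sentence that defines the outcomes with wording such as:

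> For each outcome measured at both visits, the post-test value (or, equivalently, the change) is regressed on the group indicators with the baseline value of the same outcome as covariate, within the FIML model; raw change is reported descriptively.

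Restricting the rule to outcomes measured at both visits leaves out the Diet items, which have no baseline. The power paragraph should also state the assumed pre/post correlation and the scale on which f = 0.25 is defined.

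The cost is one sentence in the plan and one degree of freedom per model. No new data, visits or participants are needed.
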